#### **5.5.1.4. Combined PRO and FCP outcome**

As a secondary outcome, we will assess the proportion of patients achieving combined clinical remission based on the sCDAI and reduction in FCP using the same criteria described above.

#### **5.5.1.5. PROMIS measures**

The Patient Reported Outcome Measurement System (PROMIS) questionnaire contains several measures previously shown to correlate with disease activity and to have construct validity in CD. These include measures of fatigue, pain interference, and sleep. PROMIS items are calibrated using a T score such that 50 is the mean for the general US population with a standard deviation of 10. Higher scores reflect greater level of the domain.

#### **5.5.1.6. Physical function and joint pain**

Physical function and joint pain will be assessed with a subset of core variables found in the Multi-dimensional Health Assessment Questionnaire (MD-HAQ). We will screen for inflammatory back pain using the criteria developed by Sieper et al. and assess symptom severity with the Bath AS Functional Index in those who screen positive.

### **5.5.2. Statistical analysis for primary and secondary outcome measures**

The primary analysis will compare the proportion of patients who achieve a symptomatic remission (aim 1) and reduction of inflammation (aim 2) at week 6 using the Cochran-Mantel-Haenszel (CMH) chisq test, which is equivalent to the score test derived from the conditional logistic regression with treatment

strata as the conditioning factor. All patients who are withdrawn or lost to follow-up prior to week 6 will be considered treatment failures. The MSD will be considered the reference group for all analyses. Although randomization should minimize unbalance between the groups, it is still possible that unbalance may occur. As such, we will use stratified analyses and conditional logistic regression analysis to adjust for potential unbalance between the two groups as observed in the descriptive analyses. Age, sex, smoking status, duration of CD, presence of disease involving the colon and/or rectum, use of corticosteroids during the trial, current use of biologic therapy, and current use of immunomodulator therapy will be examined individually for potential confounding of the main outcome using logistic regression analysis. All variables that affect the crude estimate of the relative risk of effectiveness by 10% or greater will be included in the final model.

Stratified analyses will be used to assess for treatment effect heterogeneity based on the following variables: duration of CD (as EEN appears to work better in newly diagnosed patients), presence of colonic and/or rectal disease (EEN has been hypothesized to work better in patients with only small bowel disease), and use of corticosteroids during the trial (these patients may have more severe disease). We will use the logistic regression models to look for evidence of treatment-covariate interactions. Although pre-specified, we have not powered the study for these subgroup analyses and as such they will be considered hypothesis generating. Therefore, we will report the overall results as well as results for each subgroup. We note that the strongest a priori hypothesis for treatment effect heterogeneity is with the presence or absence of inflammation. We hypothesize that the SCD may appear relatively more effective among those patients without active inflammation than among those with confirmed active inflammation at baseline.

Analysis of secondary outcomes (Secondary Aim 1): hsCRP data will be analyzed in the same manner as FCP data.

Analysis of secondary outcomes (Secondary Aim 2): The secondary outcomes of clinical remission as assessed by the CDAI, PRO2, PRO3 and combined clinical remission and resolution of inflammation will be analyzed using the same methods described for the primary outcomes. We will compare PROMIS scores at baseline and at the end of the trial using a t-test. If there are meaningful differences in baseline scores between the treatment arms, comparison of the PROMIS measures at the end of follow-up will be adjusted for the baseline value using linear regression.

Analysis of data from the Extension Phase (Secondary Aim 2): After week 6, participants will need to provide for the meals on their own if they choose to remain on the diet. This provides an opportunity to further assess the combined feasibility of the diets in the real world and patients' satisfaction with following the diet. Utilizing results from 24-hour dietary recalls, we will determine the proportion of patients assigned to each arm who elect to remain on the diet through week 12. We will also determine the proportion of patients who were able to discontinue steroid use by week 12 among the subgroup who were taking steroids in weeks 1-6. Finally, we will assess reasons for discontinuation of the diet among those who did not continue. Comparisons will be made using Fisher's exact test following the principle of intention to treat. The analysis will be repeated among the subgroup of participants who achieved remission by week 6. These results will be qualitatively compared to the free text data on satisfaction and personal experience with the diets.

Change from baseline stratified by treatment arm: For continuous outcome measures, such as sCDAI, PRO2, PRO3, and FCP, we will compare the week 6 and week 12 values to the baseline value using the Wilcoxon sign rank test, a nonparametric paired test. These analyses will be conducted separately for each treatment group. Imputation of missing data for this analysis will assume that the worst case scenario that the outcome measure was worse during follow-up than at baseline. (Note that approach to missing data for other analyses are described below).

Approach to missing data: It is possible that missing follow-up data will be more common among participants who did not have reduced symptoms, particularly those whose symptoms worsened. There are several approaches to missing data in clinical trials. Complete case analysis violates the principle of intention to treat and as such will not be employed. For continuous measures, last observation carried forward (LOCF) is the most commonly used, but it is not necessarily the most conservative. Baseline observation carried forward (BOCF) may be more appropriate, particularly in circumstances where the outcome would be expected to return to the baseline level if the treatment is discontinued. The European Medicines Agency recommends picking the most conservative approach depending on the individual trial, favoring a responder analysis (i.e. converting continuous variables to dichotomous variables) and categorizing all dropouts as treatment failures. We will use this approach in analyses for aims 1 and 2. For the continuous variables in the secondary outcomes, we will use BOCF as the most conservative

approach. Sensitivity analyses will compare results of our BOCF analysis with that obtained using LOCF or multiple imputation methods. All results will be interpreted and reported after taking into account the results of the sensitivity analyses, applying the principle put forth by the EMA to not favor the “experimental” arm, which in this RCT would be the SCD.

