## Study Summary

Title	Randomized, Multicenter, Comparative Effectiveness Trial of Specific Carbohydrate and Mediterranean Diets to Induce Remission in Patients with Crohn's Disease
Short Title	DINE-CD
IRB Number	825907
Phase	N/A
Methodology	Open Label Randomized Clinical Trial
Study Duration	3 years
Study Center(s)	Multicenter trial of up to 50 sites
Objectives	
Primary:
 

1. To compare the effectiveness of the Specific Carbohydrate Diet and a Mediterranean style diet to induce symptomatic and clinical remission in patients with Crohn's disease.

2.

 
Secondary:
 

1. To compare the effectiveness of the Specific Carbohydrate Diet and a Mediterranean style diet to reduce mucosal inflammation in patients with active Crohn's disease. Mucosal inflammation will be assessed by measuring the concentration of calprotectin in the feces (FCP).

2. To compare the effectiveness of the Specific Carbohydrate Diet and a Mediterranean style diet to reduce systemic inflammation in patients with active Crohn's disease. Systemic inflammation will be assessed by measuring the concentration of C reactive protein (CRP).

3. To compare the effectiveness of the Specific Carbohydrate Diet and a Mediterranean style diet to improve the following symptoms in patients with Crohn's disease: a) fatigue, b) pain, c) joint symptoms.

4. To determine the proportion of patients who continue the study diets when prepared food is no longer provided without cost and the reasons for discontinuation of the diets.

Number of Subjects	194 participants to be enrolled across all sites

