**Statistical Methodology**

The primary analyses for the RCT will use 2-sided tests of statistical significance and will be performed using the intention-to-treat principle. The primary analysis will compare the proportion of patients who achieve a symptomatic remission at week 6 using the Cochran-Mantel-Haenszel (CMH) chi square test . All patients who are withdrawn or lost to follow-up prior to week 6 will be considered treatment failures. The MSD will be considered the reference group for all analyses.

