### **1.5.2 This research will focus on outcomes of primary interest to patients with CD**

The proposed research will focus on two primary outcomes, resolution of the symptoms that characterize active CD and interfere with daily activities and reduction of bowel inflammation. Each of these is important to patients in their own right. Diarrhea, abdominal pain, and decline in overall wellbeing are the most common presenting symptoms for patients with CD (i.e. presence of these symptoms overcomes the inertia to ignore one's health). In our ongoing PCORI-funded study within CCFA Partners, we have confirmed that patients with CD have substantial disutility for these symptoms of CD. We surveyed 1250 patients with CD with discrete choice experiments (DCEs) using methods of conjoint analysis to estimate patients' utilities for treatment outcomes. Within the DCE, patients were asked to choose between two treatment options, each of which was described in terms of the following attributes: duration and severity of symptoms (including diarrhea, abdominal pain and general wellbeing), duration of use of steroids, and absolute increase in risk of severe infections, cancer, and need for bowel resection surgery. Our preliminary analysis demonstrates the strong negative preferences that patients have for active CD symptoms and steroid use and that the disutility is strongly tied to duration of symptoms (i.e. short periods of mild to moderate symptoms and/or steroid use are tolerable while longer periods or severe symptoms are not). We have considered this in designing our study, particularly the inclusion criteria and trial duration.

We will also examine resolution of inflammation as measured with a fecal marker, calprotectin (FCP). This biomarker is a strong predictor of another outcome of importance to patients – the duration that they will remain free of symptoms of CD. It has been repeatedly demonstrated that patients with IBD who have an elevated FCP concentration have earlier relapse of disease. Thus, we will use this

biomarker as a surrogate for future disease course. Importantly, we have demonstrated that patients highly value time in remission using similar DCE methodology. In this study, patients are willing to accept substantial risks of serious infection (approximately 18% per year) or lymphoma (approximately 0.75% per year) in exchange for 5-years without symptoms.

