## 8.2 Secondary Endpoints

### Markers of inflammation

We will compare the proportion of patients who achieve reduction in FCP to less than 250ug/g and by greater than 50% from baseline. Fecal concentration of calprotectin, a calcium binding protein found in neutrophilic granulocytes, will be measured by LabCorp. FCP concentration is correlated with endoscopic findings of mucosal inflammation and decreases following initiation of medications in active CD. There is no single standard to define mucosal healing with FCP; a recent meta-analysis identified 250 µg/g as the optimal cut point for endoscopically defined inflammation among patient with IBD. There are a number of important reasons to measure FCP in this study. From the patient's perspective, FCP predicts the risk of recurrence of symptoms for those who have achieved clinical remission through medical or surgical therapy. Equally as important, to achieve optimal adoption of dietary strategies into the management of CD will require convincing treating physicians of the effectiveness of the diet. Increasingly, physicians are demanding evidence that CD treatments improve inflammation in addition to symptoms. Thus, FCP is a biomarker that predicts an important outcome for patients and for physicians it can be used to document reduction in mucosal inflammation.

We will use hsCRP as a marker of systemic inflammation. We can compare the proportion of patients who have hsCRP below the upper limit of normal and mean levels of hsCRP as outcome measures.

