#### **3.3. Data access**

##### **TO BE COMPLETED WITH HELP FROM UNC**

During the conduct of the trial, the data management team at the University of North Carolina and the lead data analyst at the University of Pennsylvania will have access to the raw study data. Standardized reports will be generated to allow data coordinating center to monitor recruitment and retention, completion of eCRFs, and for quality control purposes prior to the end of the trial. The analyst will prepare summary documents for the investigative team without separating the data by study group. The analyst will prepare separate files stratifying the data by study group for the data and safety monitoring board (DSMB).

At the conclusion of the trial, the data analyst and study biostatistician will prepare the analytic data files to be used in the final analyses. They will work with the data coordinating center and the data management team to resolve any outstanding queries prior to conducting the final analyses. Review of descriptive data of the combined cohort may be conducted with the data management team and the data coordinating center to facilitate data cleaning.

The analytic plan will be reviewed and agreed upon by the data coordinating center and study steering committee prior to conducting the final analyses. A copy of the locked final analytic data set will be preserved as a backup. All analyses will be conducted using fast computer programs such that no changes will be made to the locked final data set.

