## 5.2. Sample size

The study is designed to enroll 97 patients into each of the treatment arms. Specific aims 1 and 2 will be considered separately and no reduction in type 1 error will be applied for multiple testing. The anticipated remission rate in the group receiving the MSD is unlikely to exceed 40% given the historical remission rates in placebo arms of Crohn's disease trials and assuming only a modest therapeutic benefit of this less restrictive of the two diets. Sample size calculations assume no loss to follow-up since all participants who are lost to follow-up will be categorized as non-responders in the analyses of both dichotomous primary outcomes (symptomatic remission and reduction in mucosal inflammation). Our PPRN Patient Governance Council met and determined that the minimum clinically important difference in remission rates is 20% as smaller differences are unlikely to justify the challenges of following a strict restriction diet such as the SCD. Thus, we used an anticipated remission rate of 40% with the MSD and 60% with the SCD to determine the sample size. With 97 participants per group, the study will have 80% power with a type 1 error of 5% to detect a difference of 40% vs 60% in effectiveness of the two diets using a chi test.

In reality, we anticipate that the remission rate in the MSD will be less than 40%. The power curve shown below depicts the power to detect a 20% difference based on the remission rate in the MSD arm of the trial where  $p_1$  represents the remission rate in the SCD arm (i.e.,  $p_1=0.3$  represents power to detect a difference of 10% vs 30% across a sample size ranging from 60 to 120). With 97 participants per group, there is more than 90% power to detect a difference of 10% vs 30% and 80% power to detect a difference of 40% vs 60%.

Finally, all of the power estimates are likely slight under estimates. We expect even more power when the Cochran-Mantel-Haenszel (CMH) chi test is used since we expect that the odds ratios in different strata are in the same direction.

Viewed alternatively, with 97 participants per arm, there is 80% and 90% power to detect the following differences based on the effectiveness of the control diet (i.e. the MSD).

Proportion of MSD group achieving the outcome	80% power to detect an absolute difference (SCD - MSD) greater than or equal to	90% power to detect an absolute difference (SCD - MSD) greater than or equal to
10%	15%	18%
20%	18%	21%

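### The documents disagree on whether FCP reduction is a second primary outcome tested at an unadjusted 5% or a secondary, exploratory one

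*Combined protocol and SAP*

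**What the plan says.** Three places treat FCP reduction as a second primary outcome.

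- Protocol 1.5.2: "The proposed research will focus on two primary outcomes". It then names symptom resolution and reduction of bowel inflammation.
- SAP 5.2, on loss to follow-up, refers to "both dichotomous primary outcomes (symptomatic remission and reduction in mucosal inflammation". It also states: "Specific aims 1 and 2 will be considered separately and no reduction in type 1 error will be applied for multiple testing". Appendix C 1.1 repeats that sentence.
- SAP 5.5.2: the primary analysis, by CMH test, covers "symptomatic remission (aim 1) and reduction of inflammation (aim 2) at week 6".

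Weaker support comes from protocol 11.2 and Appendix C 5, which call FCP the primary outcome of aim 2, and from the plural primary outcomes in SAP 2 and SAP 5.5.

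More places treat it as secondary.

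- Study Summary: the objective "To compare the effectiveness of the Specific Carbohydrate Diet and a Mediterranean style diet to reduce mucosal inflammation" is listed under Secondary, and the methodology row says "The primary analysis will compare the proportion of patients who achieve a symptomatic remission at week 6".
- Protocol 2 has one primary aim and calls the secondary aims exploratory. Protocol 2.3 lists mucosal inflammation, measured by FCP, as a secondary objective, and 3.4.1 gives symptomatic remission as the only primary endpoint.
- Protocol 8.2, under Secondary Endpoints: "We will compare the proportion of patients who achieve reduction in FCP to less than 250ug/g and by greater than 50% from baseline".
- Protocol 8.4.2 confines the primary analysis to symptomatic remission and names FCP reduction among the secondary outcomes.
- Appendix C 1.1 and SAP 2 list FCP as a secondary objective. SAP 5.5.1.3 defines it directly after the Secondary Endpoints heading (5.5.1.2).

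**The concern.** A trial needs one settled set of primary outcomes before results by arm are seen, and more so when it is open label. Here an analyst following SAP 5.2 and 5.5.2 would report FCP reduction as a primary result, and one following the protocol's objectives and section 8.4.2 would report it as secondary and exploratory. No testing order or other rule prevents a primary claim on FCP alone if symptomatic remission fails. A rule giving the SAP precedence over the protocol would not help, because the SAP carries both labels.

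The conflict also reaches the analysis lists. Protocol 8.4.2 includes FCP reduction among the secondary outcomes, but the matching list in SAP 5.5.2 omits it. The only between-arm test that the SAP specifies for FCP reduction as a stand-alone outcome is therefore inside the primary analysis.

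**Working it through.** **Does aim 2 in SAP 5.5.2 mean FCP?** The sentence says only inflammation. SAP 5.2 says mucosal inflammation, protocol 2.3 and SAP 2 define that by FCP, protocol 11.2 and Appendix C 5 tie aim 2 to FCP, and SAP 5.5.2 handles hsCRP separately as secondary. So it does.

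**The plan's own power figure.** Inputs from SAP 5.2: 97 per arm, two-sided 5%, chi-square test, 40% vs 60%. With the normal approximation and no continuity correction,

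power = Φ[(|p₁ − p₂|√n − 1.96√(2p̄(1 − p̄))) / √(p₁(1 − p₁) + p₂(1 − p₂))], where p̄ is the mean of p₁ and p₂.

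- 40% vs 60%: (0.2 × 9.849 − 1.96 × 0.7071) / 0.6928 = 0.843, so power is 80.0%.
- 10% vs 30%: (1.970 − 1.96 × 0.5657) / 0.5477 = 1.572, so power is 94.2%.

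Both agree with SAP 5.2 (80%, and more than 90%). The sample size is sound for one test at 5%.

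**Error rate if both are primary and success on either is claimed, with no true difference on either.**

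- Independent tests: 1 − 0.95² = 9.75%.
- Correlated tests: 1 − P(|Z₁| < 1.96, |Z₂| < 1.96), bivariate normal. The documents give no correlation; at assumed values of 0.2, 0.4, 0.6 and 0.9 the result is 9.6%, 9.3%, 8.8% and 7.0%.
- Upper bound: 5% + 5% = 10%.
- Errors favouring the SCD only, independent tests: 1 − 0.975² = 4.9%, against 2.5% for one test.

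**Power for FCP.** SAP 5.5.1.3 excludes patients with baseline FCP below 250 mcg/g, so fewer than 97 per arm are analysed if any such patients enrol. The documents give neither the share remaining nor FCP response rates. The shares below are assumed, and the MSD rates of 10% to 40% are borrowed from the table in SAP 5.2. Numbers per arm are 97 × 0.7, 0.5 and 0.4, rounded.

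| MSD vs SCD | 97 per arm | 68 (70%) | 48 (50%) | 39 (40%) |
|---|---|---|---|---|
| 10% vs 30% | 94% | 84% | 69% | 60% |
| 20% vs 40% | 87% | 73% | 57% | 49% |
| 30% vs 50% | 82% | 67% | 52% | 44% |
| 40% vs 60% | 80% | 65% | 50% | 42% |

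**The case against.** - **The non-adjustment is declared.** SAP 5.2 and Appendix C 1.1 say the aims are considered separately. That can be read as two questions with two conclusions, each at 5%, which is defensible. No passage promises a 5% family-wise error or says that either outcome suffices. This stands: the 9.75% is conditional on claiming success on either. But the declaration concerns alpha, not whether FCP is primary, and it fits poorly with aims called exploratory.
- **The test and p-value are the same under either label.** Largely true, since protocol 8.4.2 analyses the secondary outcomes by the primary method. The dispute is over what may be claimed from the p-value.
- **SAP 5.5.1.3 already describes a secondary FCP comparison.** It does, but it names no test. The specified test is in the primary analysis of SAP 5.5.2.
- **This looks like incomplete editing.** The primary objective lists each carry an empty item 2, and protocol 8.3 gives the sample-size paragraph of Appendix C 1.1 without the no-adjustment sentence. FCP may well have been moved to secondary with older wording left behind. That is inference, and the surviving wording is operative.
- **There is a review step.** SAP 3.3 says: "The analytic plan will be reviewed and agreed upon by the data coordinating center and study steering committee prior to conducting the final analyses". That is an occasion to settle the label; it does not settle it.
- **The FCP power loss arises under either label.** True, but SAP 5.2 applies its no-loss assumption to both primary outcomes and gives no separate power for the reduced FCP set.

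**Conclusion.** The concern holds. Current text in the protocol and the SAP gives two incompatible answers on whether FCP reduction is primary, and the SAP contradicts itself. The main test on symptomatic remission, its 5% alpha and its 80% power for 40% vs 60% are unaffected.

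If both outcomes count as primary and success on either is claimed, the chance of a false primary result is between 7.0% and 9.75% over the assumed correlations of 0 to 0.9, and never above 10%. Power for a 20-point FCP difference is between 42% and 84% when 40% to 70% of patients remain; that range rests on assumed shares and borrowed response rates. The conflict must be resolved before the final analyses.

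**What to change.** Name sCDAI symptomatic remission at week 6 as the sole primary outcome, at two-sided 5%. Then:

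- Correct protocol 1.5.2 and 11.2, Appendix C 1.1 and 5, and SAP 2, 5.2, 5.5 and 5.5.2, including the plural primary outcomes in protocol 8.4.2 and SAP 5.5.2.
- Say in the primary objective that remission is measured by the sCDAI. It now names clinical remission too, and protocol 3.4.2.1 makes CDAI remission secondary.
- In SAP 5.5.2, take FCP out of the primary analysis and add it to the secondary list with the same CMH test. The instruction to analyse hsCRP like FCP then keeps its referent.
- Align the aim numbers in protocol 8.4.2 and SAP 5.5.2 with the objectives. SAP 5.5.2 makes hsCRP Secondary Aim 1, while SAP 2 puts FCP first and CRP second.
- Reword the missing-data paragraphs in both documents, which refer to aims 1 and 2, so that the non-responder rule covers the primary outcome and the dichotomous secondary outcomes.
- Replace the no-adjustment sentence in SAP 5.2 and Appendix C 1.1 with a statement that secondary outcomes are tested at an unadjusted 5% and are exploratory.

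If FCP is to stay confirmatory, test it in fixed sequence, only after symptomatic remission is significant, and state its power for the FCP-eligible subset. A 2.5% split would instead cut the power for remission at 97 per arm to 71.1% for 40% vs 60%, and 118 per arm would be needed for 80%.

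The cost is wording only; sample size and primary power do not change. The one loss is that FCP can no longer be claimed as a stand-alone primary result.

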### **3.3 Allocation to Interventional Group**

Participants who meet all eligibility requirements, provide a baseline stool sample, and complete 5 to 7 days of sCDAI online surveys, will be randomly assigned to one of the study diets in a 1:1 ratio of SCD:MSD. The randomization will be stratified based on whether the participant is currently using a biologic therapy for CD. As such, there will be two strata as follows:

Biologic Therapy
Yes
No

Randomization will be blocked using variable block sizes ranging from 2 to 4. A study biostatistician at the DCC will generate the randomization scheme which will be incorporated into the study data management system. Once the randomization form is completed in the data management system it will generate the participants' study diet assignment.

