### **5.5. Efficacy Analysis**

Analysis of the primary outcome: The primary outcomes will be measured at 6 weeks after the start of the study diets. The primary analyses for the RCT will use 2-sided tests of statistical significance and will be performed using the intention-to-treat principle. Thus, patients will be classified according to the study arm that they were assigned, regardless of the amount of food from the assigned diet consumed.

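### The 10% rule for admitting covariates to the adjusted model does not say whether it applies to the risk ratio or the odds ratio, and that choice largely decides whether anything is adjusted for

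*Combined protocol and SAP*

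**What the plan says.** SAP 5.5.2 makes the Cochran-Mantel-Haenszel (CMH) test the primary analysis, with "strata as the conditioning factor"; SAP 5.5 adds that "The primary analyses for the RCT will use 2-sided tests of statistical significance". Adjustment is then described in two sentences.

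- For imbalance seen in the descriptive tables: "we will use stratified analyses and conditional logistic regression analysis to adjust for potential unbalance between the two groups". No threshold is given.
- For confounding, eight variables are listed: age, sex, smoking, disease duration, colonic or rectal involvement, and "use of corticosteroids during the trial, current use of biologic therapy, and current use of immunomodulator therapy". The SAP's plan for each of the eight is that it "will be examined individually for potential confounding of the main outcome using logistic regression analysis". The selection rule follows: "All variables that affect the crude estimate of the relative risk of effectiveness by 10% or greater will be included in the final model".

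Protocol 8.4.2 carries the same list and the same rule. Both documents extend the primary methods to the secondary remission outcomes (CDAI, PRO2, PRO3, and remission combined with resolution of inflammation).

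On the design side, protocol 3.3 states: "The randomization will be stratified based on whether the participant is currently using a biologic therapy for CD". It also states: "Randomization will be blocked using variable block sizes ranging from 2 to 4".

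The documents do not say how a relative risk is to be taken from a logistic model, whether the 10% refers to the risk ratio, the odds ratio or the coefficient, or what standing the final model has beside the CMH test.

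**The concern.** The rule names one measure and uses a model that produces another. Remission is expected to be common, so the two are far apart. They also respond differently to adjustment. The risk ratio standardised over the whole sample moves only if arms differ on the covariate. The odds ratio is non-collapsible: it moves away from 1 when any prognostic covariate is added, even with exact balance. A 10% shift in the odds ratio is therefore not evidence of confounding.

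Two analysts following the same sentence could report different adjusted effects, one with no covariates and one with several. The randomisation factor is on the screening list, so its place in the model depends on an imbalance that the design removes. The model is also chosen by its effect on the treatment estimate, after that estimate has been seen. One candidate, corticosteroid use during the trial, is not defined as a baseline variable, while a needed steroid increase is part of the outcome definition (protocol 3.4.1.1, SAP 5.5.1).

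**Working it through.** **1. The plan's own figure.** Inputs from SAP 5.2: 40% vs 60%, two-sided 5%, 80% power, chi-square test.

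n per arm = [1.960·√(2·0.5·0.5) + 0.842·√(0.4·0.6 + 0.6·0.4)]² / 0.20² = (1.386 + 0.583)² / 0.04 = 96.9, so 97. The plan's figure is reproduced and does not depend on the 10% rule.

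**2. The two scales at the design rates.** Risk ratio = 0.60/0.40 = 1.50. Odds ratio = (0.60/0.40)/(0.40/0.60) = 2.25. Comparing an adjusted odds ratio with a crude risk ratio would pass 10% almost mechanically (2.25/1.50 is a 50% difference before any adjustment).

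**3. Non-collapsibility with no confounding.** Take a binary covariate, 50:50 in both arms, with assumed odds ratio 4 for remission. In the MSD arm the two subgroup rates a and b must satisfy (a + b)/2 = 0.40 and b/(1−b) = 4·a/(1−a). This gives 3a² + 2.6a − 0.8 = 0, so a = 0.2408 and b = 0.5592. The same equations with mean 0.60 give 0.4408 and 0.7592 in the SCD arm. The conditional treatment odds ratio is

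(0.4408/0.5592) / (0.2408/0.7592) = 0.788/0.317 = 2.485,

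and it is the same in the other subgroup. The shift is 2.485/2.25 − 1 = 10.5%. The standardised risk ratio stays at 0.60/0.40 = 1.50.

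**4. How often the rule admits anything.** Simulation of 600 trials per setting: 194 participants, blocks of 2 or 4 within biologic strata, eight independent binary covariates added singly to a logistic model. Assumed, because the documents do not give them: prevalences 0.2 to 0.6 and one common prognostic odds ratio for all eight. Monte Carlo standard error is at most √(0.25/600), about 2 points. Chance that at least one covariate qualifies at 40% vs 60%:

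| Assumed prognostic odds ratio | Risk ratio (standardised) | Odds ratio | Log odds ratio |
|---|---|---|---|
| 1 | 0% | 4% | 14% |
| 1.5 | 0.2% | 22% | 38% |
| 2 | 1.0% | 47% | 62% |
| 3 | 2.2% | 76% | 83% |

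Repeating the simulation gave 0.3-3% (risk ratio) and 22-78% (odds ratio) over prognostic odds ratios 1.5 to 3.

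Other rates, for prognostic odds ratios 1.5 / 2 / 3:

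- 20% vs 40%: risk ratio 4.2 / 8.7 / 21.0%; odds ratio 26.8 / 54.0 / 81.7%.
- 40% vs 40%: risk ratio 1.2 / 3.8 / 8.7%; odds ratio 11.8 / 32.3 / 53.2%.

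**5. The biologic stratum.** Blocks of at most 4 at 1:1 leave an imbalance of at most 2 patients per stratum. The worst case (+2 in one stratum, −2 in the other) at 40% vs 60% gives a crude risk ratio of 1.511 against 1.500 adjusted if the stratum odds ratio is 2 (0.7%), and 1.532 against 1.500 if it is 10 (2.1%). In the simulations the stratum qualified in 0% of trials on the risk-ratio scale in every setting. On the odds-ratio scale it qualified in 0-4.5% of trials at 40% vs 60% and in up to 9.5% at 20% vs 40%. With perfect balance and stratum prevalence 30-50%, the expected odds-ratio shift at 40% vs 60% is 2.0-2.5% (stratum odds ratio 2), 5.1-6.4% (3), 8.2-10.5% (4) and 11.1-14.5% (5). Entry there comes essentially from non-collapsibility.

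**The case against.** The strongest reply is that little hangs on the rule. The candidates and the threshold are prespecified and a published method is cited. The primary result is the CMH test, which this screening does not touch. The only strata in the design are biologic use yes or no, so the CMH test, and any conditional logistic model built on the same strata, may already condition on that factor. This stands, and it limits the point to the supportive adjusted estimates. The SAP does not name the strata, however, and the rule still lists the stratum among the variables to be screened.

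Four stronger readings are tempting, and the documents do not support them.

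- A reader might infer that the stratum can never enter. That is too strong. It can enter on the odds-ratio scale (step 5). Even on the risk-ratio scale a contrived case crosses 10%: a stratum of 20 patients holding nearly all remissions gives 1.20 crude against 1.00 adjusted.
- A reader might infer that the 10% rule is the sole route to adjustment. The text says that qualifying variables are included; it does not say that no others are, and the imbalance clause is a separate route.
- A reader might infer that the risk-ratio rule hardly ever fires. That depends on the base rate and on prognostic strength. SAP 5.2 expects MSD remission below 40%, and at 20% vs 40% the rule fires in up to about 21% of trials.
- A reader might infer a loss of power for the trial. Power at the design rates is 80% for the unadjusted comparison. Any gain from covariates depends on prognostic strengths that the documents do not give.

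**Conclusion.** The point holds as a cheap improvement to the supportive analysis. The rule as written does not define one analysis. At 40% vs 60%, with prognostic odds ratios of 1.5 to 3, it admits at least one covariate in about 0-3% of trials on one reading and about 20-80% on the other. On the second reading, entry need not reflect confounding.

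The percentages rest on assumed prevalences and on one common, independent effect for all eight covariates. The scale mismatch and the 10.5% example do not rest on the simulation. If no covariate is prognostic, the gap is small on these two scales (0% against 4%).

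The reach is the adjusted estimate for the primary outcome and for the secondary remission outcomes analysed in the same way. The primary CMH p-value and the sample size are unaffected.

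**What to change.** In SAP 5.5.2 and protocol 8.4.2, delete the 10% rule and the one-at-a-time screening. Replace them with one covariate set fixed now: the biologic randomisation stratum always, plus the other listed variables as measured at baseline. For corticosteroids, use baseline use (already in the SAP section 4 baseline table) in place of use during the trial. Fit the logistic model once. Report a standardised risk difference and risk ratio from it, labelled as supportive, beside the CMH result, so that crude and adjusted figures share a scale. In the same edit, name biologic use as the CMH stratum if that is what is meant.

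The cost is wording only: no new data, no participants and no change to the primary test. The downside is that the sponsor must commit to the covariates before seeing arm-level data. At the low end of the range in SAP 5.2 (10% vs 30%) there would be about 97·0.10 + 97·0.30 = 39 remissions for nine coefficients (treatment plus eight covariates at one each), so the text should also state a fallback if the model does not converge.
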